#### 6.3.1.16.2 Nephrotoxicity

If creatinine is greater than upper limit of normal for the patient's age, a creatinine clearance or GFR must be determined. If the creatinine clearance is <75% of normal for the patient's age, then the carboplatin dose should be held until creatinine clearance recovers to 75% of normal. Carboplatin dose should then be reduced by 25%.

#### 6.3.1.16.3 Hepatotoxicity

If Grade 3-4 hepatotoxicity develops during maintenance, hold chemotherapy until toxicity is less than Grade 2. If the etiology of the toxicity is unexplained, then the dose of vincristine and carboplatin should be reduced by 25%.

Page 91

#### 6.3.1.16.4 Neurotoxicity

#### Seizures

**Novartis** 

For seizure due to vincristine, hold one dose, then resume at 1.0 mg/m^2 (1.5 mg max) while on anticonvulsants. If seizures do not recur, escalate to full dose. For seizures not associated with vincristine, place patient on anticonvulsants after appropriate neurological evaluations, and proceed with chemotherapy at full doses.

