#### 5.2 Inclusion criteria

Patients eligible for inclusion in this study have to meet all of the following criteria:

- 1. Male or female between ≥12 months and <18 years of age at the time of signing the informed consent form. Patients under 6 years old must weigh at least 7 kg at the time of enrollment. Patients over 6 years old must weigh at least 10 kg at the time of enrollment.
- 2. **For HGG cohort only:** Relapsed, progressed, or failed to respond to frontline therapy. Frontline therapy is presumed to be optimal surgical approach (biopsy or resection) with radiation and/or chemotherapy.
  - **For LGG cohort only:** Patients with progressive disease following surgical excision, or non-surgical candidates with necessity to begin first systemic treatment because of a risk of neurological impairment with progression.
- 3. Locally determined HGG or LGG as defined by WHO histological classification system, revised 2016 (Appendix 4). For HGG cohort only: Locally confirmed histologic diagnosis of High Grade Glioma (Grade III or IV glioma), including anaplastic pleomorphic xanthoastrocytoma (aPXA) and anaplastic gangliogliomas.
  - **For LGG cohort only**: Locally confirmed histologic diagnosis of Low Grade Glioma (Grade I or II)
- 4. Locally determined and centrally confirmed measurable disease with minimal biperpendicular diameter that must be at least twice the imaging slice thickness to be used for efficacy assessments. (Both local and centrally confirmed results must show measurable disease to meet eligibility)
- 5. *BRAF* V600 mutation-positive tumor as assessed locally, or at a Novartis designated central reference laboratory if local *BRAF* V600 testing is unavailable.
- 6. Tumor tissue must be available and subsequently provided to Novartis for central confirmatory testing of *BRAF* mutational status (HGG and LGG cohort), and for HGG histopathology (HGG cohort).
- 7. Performance score of  $\geq$ 50% according to the Karnofsky/Lansky performance status scale.
- 8. Females of child-bearing potential must be willing to practice acceptable methods of birth control. Additionally, females of childbearing potential must have a negative serum pregnancy test within 28 days prior to day 1.
- 9. Must have adequate bone marrow function per central or local lab in the absence of growth factor support and is defined as:
  - Absolute neutrophil count (ANC) ≥1000/μL;

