## 6.1.2.1 Induction Therapy

Prior to induction, central or local lab results must be assessed to confirm ANC  $\geq 1000/\mu L$  and platelet count  $\geq 100,000/\mu L$ .

Induction will consist of 10 weeks of therapy followed by 2 weeks without chemotherapy. Induction should only be interrupted in the event of grade 3 neurotoxicity, grade 2 nephrotoxicity, grade 4 hematologic toxicity, or disease progression. See Section 6.3.1.16 for dose modification guidelines.

Carboplatin (CBDCA): 175 mg/m^2 as weekly IV infusion over 60 minutes on weeks 1 to 4, and on weeks 7 to 10, on the same day as VCR dosing

Vincristine (VCR): 1.5 mg/m^2 as weekly IV bolus infusion (0.05 mg/kg if child is <12 kg) (maximum dose of 2.0 mg) for 10 weeks.

Table 6-9 Induction therapy

| Week
1 | Week
2 | Week
3 | Week
4 | Week
5 | Week
6 | Week
7 | Week
8 | Week
9 | Week
10 | Week
11 | Week
12 |
|-----------|-----------|-----------|-----------|-----------|-----------|-----------|-----------|-----------|------------|------------|------------|
| VCR        | Rest       | Rest       |
| CBDC      | CBDC      | CBDC      | CBDC      |           |           | CBD       | CBDC      | CBDC      | CBDC       |            |            |
| Α         | Α         | Α         | Α         |           |           | CA        | Α         | Α         | Α          |            |            |

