## 6.1.2.2 Maintenance Therapy

Following induction therapy and two weeks of rest, maintenance therapy should begin if peripheral counts recover to ANC  $\geq 1,000/\mu L$  and platelet count  $\geq 100,000/\mu L$ . Repeat blood counts every 7 days until counts are adequate. Recovery of peripheral counts is required prior to starting each maintenance cycle. Local laboratory results may be used prior to dosing if a central lab is not scheduled per protocol or when central lab results will not available in time for a scheduled cycle. Results will be collected in the eCRF.

Each maintenance cycle will be 6 weeks in duration and consists of 4 weekly doses of carboplatin, and three weekly doses of vincristine given concomitantly with the first 3 weeks of carboplatin, followed by two weeks of rest. Maintenance will continue for a total of 8 cycles. See Section 6.3.1.16 for dose modification guidelines.

Carboplatin (CBDCA): 175 mg/m^2 as weekly IV infusion over 60 minutes on weeks 1 to 4 of each cycle.

Vincristine (VCR): 1.5 mg/m^2 as weekly IV bolus infusion (0.05 mg/kg if child is <12 kg) (maximum dose of 2.0 mg) on weeks 1 to 3 of each cycle, on the same day as CBDCA dosing.

Table 6-10 Maintenance therapy

| Week 1 | Week 2 | Week 3 | Week 4 | Week 5 | Week 6 |
|--------|--------|--------|--------|--------|--------|
| VCR    | VCR    | VCR    |        | Rest   | Rest   |
| CBDCA  | CBDCA  | CBDCA  | CBDCA  |        |        |

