#### Peripheral neuropathy

For peripheral neuropathy from vincristine including weakness, paresthesia, ileus requiring IV therapy, stridor or ptosis or visual change, hold vincristine until symptoms are markedly improved. Resume at 66% dose or 1.0 mg/m^2 (1.5 mg max). Escalate to full dose as tolerated. For jaw pain, constipation, mild foot drop, do not modify dose unless causing significant patient discomfort. Then the vincristine may be reduced to 80% or 1.2 mg/m^2 (1.5 m^2) and escalate as tolerated.

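### The vincristine restart dose after a seizure gives little or no reduction for children under 12 kg, who are dosed by weight rather than by body surface area

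*Protocol*

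**What the plan says.** Vincristine in the LGG chemotherapy arm has two dose bases. Section 6.1.2.1 (Induction Therapy) gives "1.5 mg/m 2 as weekly IV bolus infusion (0.05 mg/kg if child is <12 kg) (maximum dose of 2.0 mg) for 10 weeks". Section 6.1.2.2 (Maintenance Therapy) repeats both bases and the same maximum.

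The weight-based branch can be used in this trial. Section 5.2 sets the lower age limit at 12 months and adds: "Patients under 6 years old must weigh at least 7 kg at the time of enrollment".

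For a seizure attributed to vincristine, section 6.3.1.16.4 (Neurotoxicity, Seizures) says to "hold one dose, then resume at 1.0 mg/m 2 (1.5 mg max) while on anticonvulsants". It continues: "If seizures do not recur, escalate to full dose". There is no mg/kg figure and no percentage.

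The neighbouring rules are worded differently. In the same section, the peripheral neuropathy rule reads "Resume at 66% dose or 1.0 mg/m 2 (1.5 mg max"), and its milder step offers 80% or 1.2 mg/m². The encephalopathy rule cuts both drugs by 20%. The hepatotoxicity rule (6.3.1.16.3) cuts both by 25%. Each of these contains a percentage that applies at any weight.

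**The concern.** The instruction to go back up to full dose shows that the restart is meant to be lower than full dose. For a child dosed at 1.5 mg/m² it is. For a child dosed at 0.05 mg/kg, the rule replaces a weight-based dose with a surface-area dose, and nothing guarantees that the second is smaller than the first.

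At stake is the safety of the smallest children in the control arm: after a seizure attributed to the drug, the written rule may give them nearly the same dose again, or slightly more. The held dose and the anticonvulsants still protect them; the step down largely does not happen.

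**Working it through.** **Inputs from the Protocol**

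- Full dose: 1.5 mg/m², or 0.05 mg/kg under 12 kg; maximum 2.0 mg (6.1.2.1, 6.1.2.2)
- Restart after a seizure: 1.0 mg/m², maximum 1.5 mg (6.3.1.16.4)
- Lowest eligible weight 7 kg, lowest age 12 months (5.2)

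**1. Children dosed at 1.5 mg/m²**

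- BSA up to 1.33 m²: 1.0 / 1.5 = 66.7%, a cut of 33%. This reproduces the 66% in the neuropathy rule.
- BSA 1.4 m²: 1.4 mg against the capped 2.0 mg, a cut of 30%.
- BSA 1.5 m² or more: 1.5 mg against 2.0 mg, a cut of 25%.

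The rule works for these children.

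**2. Children under 12 kg, Protocol figures only**

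Full dose = 0.05 × W mg. Restart = 1.0 × BSA mg. The two are equal when BSA = 0.05 × W, and the restart is the larger dose at any BSA above that.

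- 7 kg: full dose 0.350 mg, equal at 0.350 m²
- 9 kg: full dose 0.450 mg, equal at 0.450 m²
- 11.9 kg: full dose 0.595 mg, equal at 0.595 m²

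The 1.5 mg cap never binds, because full dose stays below 0.6 mg.

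**3. Size, with an assumed BSA**

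The Protocol gives neither heights nor a BSA formula. Assume Mosteller, BSA = √(H × W / 3600), with H in cm and W in kg. Then

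restart / own dose = √(H × W / 3600) / (0.05 × W) = √(H / (9 × W)).

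The restart is a rise whenever H exceeds 9 × W. With an assumed height range at each weight:

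| Weight (kg) | Assumed height (cm) | Own dose (mg) | Restart (mg) | Restart against own dose | A rise if height exceeds (cm) |
|---|---|---|---|---|---|
| 7 | 64–72 | 0.350 | 0.353–0.374 | +1% to +7% | 63 |
| 8 | 66–76 | 0.400 | 0.383–0.411 | −4% to +3% | 72 |
| 9 | 68–82 | 0.450 | 0.412–0.453 | −8% to +1% | 81 |
| 10 | 70–85 | 0.500 | 0.441–0.486 | −12% to −3% | 90 |
| 11.9 | 76–92 | 0.595 | 0.501–0.551 | −16% to −7% | 107.1 |

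**4. How far the answer depends on the assumption**

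- A weight-only formula, BSA = (4W + 7) / (W + 90), gives 0.361 / 0.350 = 103% of own dose at 7 kg, 0.470 / 0.500 = 94% at 10 kg and 0.536 / 0.595 = 90% at 11.9 kg.
- Under Mosteller, a restart at two-thirds of own dose needs √(H / (9W)) = 2/3, so H = 4 × W: 28 cm at 7 kg and about 48 cm at 11.9 kg. Neither is possible at 12 months or older.
- Even an extreme child of 11.9 kg and 64 cm would restart at √(64 / 107.1) = 77% of own dose.

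**5. Across the 12 kg line**

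At heights of 76–92 cm, a 12.0 kg child has a BSA of 0.503–0.554 m². Full dose is 0.755–0.831 mg and the restart 0.503–0.554 mg, a cut of 33%. At 11.9 kg and the same heights the restart is almost the same, 0.501–0.551 mg, but it follows a full dose of 0.595 mg, a cut of only 7% to 16%.

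**The case against.** No figure in the seizure rule is miscalculated: 1.0 / 1.5 is two-thirds. What is missing is a branch for one subgroup, and a clinician could infer it. The neuropathy rule in the same section pairs 1.0 mg/m² with 66%, and the return to full dose implies that the restart must be lower. Section 6.3.1 describes the chemotherapy modifications as general guidelines, section 6.1.2 points to local labels, and section 4.1 refers to institutional practice.

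The percentages also rest on an outside BSA formula and assumed heights. On those heights a rise throughout the range appears only at 7 kg; the sign changes at 8 and 9 kg, and at 10 kg and above there is some cut.

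Finally, 0.05 mg/kg is already about 0.9 to 1.2 mg/m² on the same assumption (0.350 / 0.374 = 0.94; 0.595 / 0.501 = 1.19). Small children therefore start lower per m² and end at the same level as others after a seizure.

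Much of this is fair. It is a gap in a rule, not a wrong sum, and a rise in dose is not the general result. But the 66% option belongs to another toxicity and is not in the seizure rule, and general references to labels and practice do not replace an explicit dose. A lower starting level per m² does not explain a rule that resumes treatment and then escalates: under 12 kg there is little or nothing left to escalate to. The break-even in step 2 needs no outside assumption.

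**Conclusion.** The point holds. Followed as written, the seizure rule gives children under 12 kg roughly 84% to 107% of the dose that preceded the seizure, against 67% to 75% for all other children. That range rests on Mosteller and the assumed heights. The conclusion that a two-thirds restart cannot be reached holds at any realistic height under that formula, and the weight-only formula agrees.

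The reach is narrow: a child under 12 kg, in the control arm of about 34 (one-third of 102), with a seizure attributed to vincristine. The Protocol gives no weight distribution or seizure rate, so no count can be given. Sample size, endpoints and analyses are unaffected. It should be fixed because it concerns patient safety and the correction is simple.

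**What to change.** In the seizure rule of section 6.3.1.16.4, state that 1.0 mg/m² (maximum 1.5 mg) applies to children dosed at 1.5 mg/m², and add: *Children dosed at 0.05 mg/kg resume at 66% of their own full dose (about 0.033 mg/kg).* This gives 0.033 × 7 = 0.231 mg at 7 kg and 0.033 × 11.9 = 0.393 mg at 11.9 kg. If the sponsor prefers another level, it should be written as a fraction of the child's own dose and be clearly below it.

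The neuropathy rule needs no correction, since its percentages already work at any weight. A clause directing children under 12 kg to those percentages would be an optional clarification.

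The cost is one sentence. Nothing changes for children of 12 kg or more, or for any analysis.

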#### **Encephalopathy**

Neither carboplatin nor vincristine commonly cause encephalopathy. Therefore the patient must be carefully assessed for other causes including hydrocephalus, shunt malfunction, overhydration, too rapid withdrawal of steroids, syndrome of inappropriate antidiuretic hormone secretion (SIADH), hypothalamic dysfunction, hemorrhage, anticonvulsant toxicity, etc. If a correctable cause cannot be identified, delay therapy up to 2 weeks and proceed only if patient has improved substantially. Proceed with 20% reduction of both carboplatin and vincristine.

#### Peripheral neuropathy

For peripheral neuropathy from vincristine including weakness, paresthesia, ileus requiring IV therapy, stridor or ptosis or visual change, hold vincristine until symptoms are markedly improved. Resume at 66% dose or 1.0 mg/m^2 (1.5 mg max). Escalate to full dose as tolerated. For jaw pain, constipation, mild foot drop, do not modify dose unless causing significant patient discomfort. Then the vincristine may be reduced to 80% or 1.2 mg/m^2 (1.5 m^2) and escalate as tolerated.

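### The milder vincristine neuropathy reduction prints its dose cap as an area (1.5 m²), so the mg/m² form has no valid mg cap of its own

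*Protocol*

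**What the plan says.** Full-dose vincristine in the LGG chemotherapy arm is 1.5 mg/m² weekly with a 2.0 mg maximum. Section 6.1.2.1 sets this for induction ("0.05 mg/kg if child is <12 kg) (maximum dose of 2.0 mg) for 10 weeks") and section 6.1.2.2 for maintenance ("maximum dose of 2.0 mg) on weeks 1 to 3 of each cycle").

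Section 6.3.1.16.4 then gives reduced doses in several situations:

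- **Seizure due to vincristine:** resume at 1.0 mg/m², with the limit "1.5 mg max) while on anticonvulsants".
- **Stronger neuropathy tier** (weakness, paresthesia, ileus needing IV therapy, and similar): hold until markedly improved, then "Resume at 66% dose or 1.0 mg/m"², again with a 1.5 mg maximum in parentheses.
- **Milder neuropathy tier** (jaw pain, constipation, mild foot drop): no change unless there is significant discomfort, in which case "the vincristine may be reduced to 80% or 1.2 mg/m"². The parenthesis here reads 1.5 m², without mg and without the word max.

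No other section gives a cap for the milder tier.

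**The concern.** The parenthesis in the milder tier stands where the two parallel rules state a dose limit in mg. It holds a unit of area instead, so a site cannot apply it as a dose limit. A prescriber who uses the mg/m² form has to guess. The figure could be a misprint for 1.5 mg, a ceiling on the body surface used in the calculation, or something to disregard.

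These guesses lead to different doses in larger adolescents, and two of them weaken or remove the intended reduction. The drug is neurotoxic and the patients concerned already have neuropathy. Section 12 allows no authorised deviations, so the printed rule should not need interpretation.

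**Working it through.** **Inputs.** Full dose is 1.5 mg/m² up to 2.0 mg (sections 6.1.2.1 and 6.1.2.2). The milder tier is 80% or 1.2 mg/m², and the stronger tier is 66% or 1.0 mg/m² with a 1.5 mg maximum (section 6.3.1.16.4). Patients are eligible up to but not including 18 years (section 5.2). The protocol gives no body-surface (BSA) values, so the range of 1.25 to 1.80 m² below is an assumption.

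**Step 1: the printed rates.** 0.80 × 1.5 = 1.20 mg/m² and 0.66 × 1.5 = 0.99, about 1.0 mg/m². The percent and mg/m² figures agree as long as the full dose is not capped.

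**Step 2: where the full dose is capped.** 2.0 / 1.5 = 1.33 m². Above this the percent form of the milder tier is fixed at 0.80 × 2.0 = 1.60 mg.

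**Step 3: the milder tier under each reading of the parenthesis.**

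- Percent form: 0.80 × min(1.5 × BSA, 2.0)
- Body-surface ceiling: 1.2 × min(BSA, 1.5)
- Parenthesis ignored: min(1.2 × BSA, 2.0), since the general maximum still applies
- Misprint for 1.5 mg: min(1.2 × BSA, 1.5)

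| BSA (m²) | Full dose (mg) | Percent form | Ceiling at 1.5 m² | Parenthesis ignored | 1.5 mg cap |
|---|---|---|---|---|---|
| 1.25 | 1.875 | 1.50 | 1.50 | 1.50 | 1.50 |
| 1.33 | 2.00 | 1.60 | 1.60 | 1.60 | 1.50 |
| 1.40 | 2.00 | 1.60 | 1.68 (84%) | 1.68 (84%) | 1.50 (75%) |
| 1.50 | 2.00 | 1.60 | 1.80 (90%) | 1.80 (90%) | 1.50 (75%) |
| 1.60 | 2.00 | 1.60 | 1.80 (90%) | 1.92 (96%) | 1.50 (75%) |
| 1.67 | 2.00 | 1.60 | 1.80 (90%) | 2.00 (100%) | 1.50 (75%) |
| 1.80 | 2.00 | 1.60 | 1.80 (90%) | 2.00 (100%) | 1.50 (75%) |

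Percentages are of the full dose. With the parenthesis ignored, the reduction disappears at 2.0 / 1.2 = 1.67 m².

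**Step 4: what remains once the unit is corrected to 1.5 mg.** In the milder tier the forms part above 1.5 / 1.2 = 1.25 m². The gap reaches 1.60 − 1.50 = 0.10 mg at 1.33 m² and stays there. In the stronger tier, from 1.5 m² upward, the percent form gives 0.66 × 2.0 = 1.32 mg and the mg/m² form gives 1.50 mg, a gap of 0.18 mg.

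**The case against.** The strongest reply is that this is a misprint most readers would correct for themselves. The same paragraph prints 1.5 mg max a few lines earlier, and the seizure rule repeats it. The percent form comes first in the sentence, works for every patient without the parenthesis, and never exceeds 1.60 mg. The milder reduction is optional, both tiers allow re-escalation, and section 6.1.2 also refers sites to local labels. The control arm is about 34 patients (102 × 1/3). Only those with milder neuropathy, a body surface above about 1.33 m² and a prescriber using the mg/m² form could receive more than the percent form gives.

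All of that stands and keeps the point minor. It does not make the printed limit valid. A conversion slip in the PDF text is unlikely, because the superscript is explicit and the word max is missing too, but the page itself should be checked.

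A reader might go further and infer that the two forms contradict each other even after correction, or that the two neuropathy tiers collapse into one because both mg/m² forms give 1.50 mg from 1.5 m². The protocol does not support either. The word *or* offers two permitted reductions, and all results lie between 66% and 80% of the full dose. A result of 75% matches the protocol's own 25% vincristine reduction for unexplained hepatotoxicity. The tiers also still differ in handling: the stronger one requires vincristine to be held until symptoms are markedly improved.

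**Conclusion.** The unit error is real and sits in an operative dosing instruction. It leaves the mg/m² form of the milder tier without a valid cap of its own. Under the readings the text leaves open, the mg/m² form could give a larger adolescent 1.80 mg or up to the full 2.0 mg, against 1.60 mg by percent. These sizes assume a body surface of 1.5 m² or more (1.80 mg) and about 1.67 m² or more (2.0 mg). The number of patients affected is unknown.

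Three further inferences should not be drawn:

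- **Doses above 2.0 mg.** At 1.80 m² the bare product is 1.2 × 1.80 = 2.16 mg, but nothing in the neuropathy paragraph lifts the general 2.0 mg maximum.
- **No reduction in children under 12 kg.** They are dosed at 0.05 mg/kg, so 1.2 mg/m² would equal the full dose at some body surface, for example 0.50 / 1.2 = 0.417 m² at 10 kg. Whether any child reaches that surface depends on values the protocol does not give, and the percent form covers these children.
- **The percentage must govern.** Ruling that the percentage governs, with the 1.5 mg cap kept as an upper limit, would change dosing. It would withdraw the 1.50 mg now permitted in the stronger tier and make that tier's printed cap redundant. It would still give 75%, not 80%, in the milder tier at the cap.

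Severity is minor. ORR, power, alpha and the primary analysis are unaffected.

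**What to change.** In section 6.3.1.16.4, Peripheral neuropathy, replace the parenthesis 1.5 m² in the milder tier with the intended mg cap. This is most likely 1.5 mg max, to be confirmed against the COGA9952 regimen that sections 1.2.4 and 2.5 name as the source. The cost is one line at the next amendment, plus a short clarification to sites with patients on vincristine if the amendment is not imminent.

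Optional, and not a correction of an error: the sponsor may wish to say which form applies once the 2.0 mg maximum is reached, since the percent and mg/m² forms then differ slightly. The seizure rule needs no change.

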#### 6.3.1.16.5 Allergic reactions

Allergic reactions may occur in 10 to 30% of children receiving frequent carboplatin. These reactions can include facial flushing, urticaria, agitation, abdominal pain, edema, and sometimes bronchospasm leading to hypoxia and even respiratory arrest.

Patients receiving carboplatin should be monitored by an experienced nurse throughout the infusion and for 1 hour after.

Patients with any respiratory compromise as a result of carboplatin therapy should not receive carboplatin again and will be discontinued from the study. They will continue into posttreatment follow up.

Patients with mild or questionable reactions without respiratory compromise may continue on therapy with pre-treatment as per below.

Carboplatin allergies should be documented as an adverse event in the eCRF.

Carboplatin should always be given in a setting with rapid access to pediatric advanced lifesupporting support capability.

Consideration should be given to provide effective measures to prevent any recurrences of allergic reactions.

The following are offered as a supplement to institutional practice. If an allergic reaction occurs it should be treated as for any other drug reactions as follows:

- 1. Stop the carboplatin infusion
- 2. Rapid assessment and management of the airway
- 3. If airway compromise or acute bronchospasm, give Epinephrine 0.01 ml/kg (maximum 0.5 mL) of 1:1000 solution SQ and repeat in 20 minutes if necessary.
- 4. Albuterol inhaled can be used to treat resistant bronchospasm.
- 5. Diphenhydramine 1-2 mg/kg slow IV will help shorten the duration of the reaction, but does not have an immediate effect.
- 6. Glucocorticoids may have no effect for 6 to 12 hours, but may help prevent relapse of severe reactions.
- 7. Patients with mild to moderate reactions (urticaria or mild bronchospasm) should be observed for a minimum of 6 hours. Those with moderate to severe reactions may relapse and should be observed in the hospital at least overnight.
- 8. Prevention of recurrence:
  - a. Children with respiratory compromise should no longer receive carboplatin and are discontinued from the study.
  - b. Children with mild or questionable reactions can continue carboplatin with close monitoring and pre-treatment with steroids and diphenhydramine. For optimal effect, give Prednisone 1 mg/kg q6 hours PO or Prednisolone 1 mg/kg IV q6 hours for 3 to 4 doses prior to carboplatin, with the last dose one hour before carboplatin. Also give diphenhydramine 1 mg/kg IV or PO one hour before carboplatin. All carboplatin should be given in a monitored setting with resuscitation drugs and equipment readily available. A guideline for desensitization and continuation of treatment if a patient's tumor is responding well to carboplatin treatment has been published (Broom 1996).

